#### **7.5.1.4. Itch Numeric Rating Scale (7-Day Recall)**

The 7-day recall Itch NRS is a daily participant-reported measure of the worst level of itch intensity. Participants will be asked to rate the itch severity of their AD by selecting a number from 0 (no itch) to 10 (worst itch imaginable) that best describes their worst level of itching in the past 7 days via the tablet during Protocol-defined clinic visits during the VCE period.

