To further evaluate the efficacy of ruxolitinib cream in participants with moderate AD who had an inadequate response to, or are intolerant to, or contraindicated to TCSs and TCIs.	
 Proportion of participants with EASI75 from baseline at each postbaseline visit except Week 8. Proportion of participants with IGA-TS from baseline at each postbaseline visit except Week 8. Proportion of participants with ITCH4 from baseline at each postbaseline visit except Week 8. Time to achieve ITCH4 during the VC period. Time to achieve ITCH2 during the VC period. (ITCH2 is defined as achieving ≥ 2-point improvement from baseline in Itch NRS score.) Change from baseline (pre-study cream application) in current Itch NRS score at 5, 15, 30, 45, and 60 minutes and 2, 4, and 6 hours post-initial dose on Day 1. Proportion of participants achieving at least a 2-point decrease from baseline in current Itch NRS score at 5, 15, 30, 45, and 60 minutes and 2, 4, and 6 hours post-initial dose on Day 1.

Table 5: Objectives and Endpoints (Continued)

Objectives	Endpoints

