
To further evaluate the efficacy of ruxolitinib cream in participants with moderate AD who had an inadequate response to, or are intolerant to, or contraindicated to TCSs and TCIs (continued).
	
 • Proportion of participants achieving at least a 4-point decrease from baseline in current Itch NRS score at 5, 15, 30, 45, and 60 minutes and 2, 4, and 6 hours post-initial dose on Day 1. • Proportion of participants with EASI50 from baseline at each postbaseline visit. (EASI50 is defined as achieving $\geq 50\%$ improvement in EASI score.) • Proportion of participants with EASI90 from baseline at each postbaseline visit. (EASI90 is defined as achieving $\geq 90\%$ improvement in EASI score.) • Proportion of participants achieving both EASI75 from baseline and IGA-TS at each postbaseline visit. • Change from baseline at each postbaseline visit for the following: 
 – AD-affected %BSA – EASI score – SCORAD score – Itch NRS score – Skin Pain NRS score • Time to open-label escape arm (defined as not achieving 50% improvement in EASI score from baseline at 2 consecutive visits at least 1 week apart) • Proportion of participants concurrently meeting all of the following criteria at each postbaseline visit: IGA score ≥ 3, EASI score ≥ 16, Itch NRS score ≥ 4, BSA $\geq 10\%$, and DLQI score > 10. • Time to concurrently meeting all of the following criteria: IGA score ≥ 3, EASI score ≥ 16, Itch NRS score ≥ 4, BSA $\geq 10\%$, and DLQI score > 10. • Proportion of participants who experience a relapse after study treatment discontinuation. (proportion of participants among EASI75 responders who are on study treatment at Week 24 who meet relapse criteria [loss of EASI50 from baseline] at the safety follow-up visit) • Time to first re-treatment during the VCE period. • Proportion of time off study treatment due to lesion clearance during the VCE period by visit. • Proportion of time on study treatment during the VCE period by visit.

Table 5: Objectives and Endpoints (Continued)

Objectives	Endpoints

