**Table 1: Objectives and Endpoints**

Objectives	Endpoints
Coprimary	
To establish the efficacy of ruxolitinib cream in participants with moderate AD who had an inadequate response to, or are intolerant to, or contraindicated to TCSs and TCIs.	
 
The binary response status of EASI75 from baseline at Week 8. (EASI75 is defined as achieving <math>\geq 75\%</math> improvement in EASI score.)
 
The binary response status of IGA-TS at Week 8. (IGA-TS is defined as achieving an IGA score of 0 or 1 with <math>\geq 2</math>-grade improvement from baseline.)
 

Key Secondary	
To further assess the treatment effects of ruxolitinib cream in participants with moderate AD who had an inadequate response to, or are intolerant to, or contraindicated to TCSs and TCIs.	
 
The binary response status of ITCH4 from baseline to Week 8. (ITCH4 is defined as achieving <math>\geq 4</math>-point improvement in Itch NRS score.)
 
The binary response status of ITCH4 from baseline to Day 7.
 
The binary response status of ITCH4 from baseline to Day 3.
 
The binary response status of ITCH4 from baseline to Day 2.
 

Secondary	
To evaluate the safety and tolerability of ruxolitinib cream in participants with moderate AD who had an inadequate response to, or are intolerant to, or contraindicated to TCSs and TCIs.	The type and severity of AEs as well as changes from baseline in vital signs and laboratory data for hematology and serum chemistry.
To further evaluate the efficacy of ruxolitinib cream in participants with moderate AD who had an inadequate response to, or are intolerant to, or contraindicated to TCSs and TCIs.	
 
The binary response status of EASI75 from baseline at each postbaseline visit except Week 8.
 
The binary response status of IGA-TS from baseline at each postbaseline visit except Week 8.
 
The binary response status of ITCH4 from baseline at each postbaseline visit except Week 8.
 
Time to achieve ITCH4 during the VC period.
 
Time to achieve ITCH2 during the VC period. (ITCH2 is defined as achieving <math>\geq 2</math>-point improvement from baseline in Itch NRS score.)
 

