### **7.4. Analysis of the Key Secondary Efficacy Parameters**

#### **7.4.1. Key Secondary Efficacy Measures**

##### **7.4.1.1. Itch Numerical Rating Scale Score**

The Itch NRS is a once-daily patient-reported measure of itch intensity assessed using an 11-point scale (0 = no itch to 10 = worst imaginable itch) that best describes their worst level of itching in the past 24 hours.

The Itch NRS score for baseline will be determined by averaging the 7 daily NRS scores directly before Day 1 (Day -7 to Day -1). The by-visit Itch NRS score for postbaseline visits will be determined by averaging the 7 daily NRS scores directly before the visit day. If 4 or more daily scores are missing (out of the 7), the Itch NRS score at the visit will be set to missing. For all daily itch related analyses, including time to achieve Itch NRS score improvement of at least 2 or 4 points analyses, baseline will be defined as the last available Itch NRS score during the week prior to Day 1 (Day -7 to Day -1).

The proportion of participants with a clinically relevant change in itch, defined as a  $\geq 4$ -point improvement in Itch NRS score from baseline to Week 8, will be summarized by treatment group for participants with baseline Itch NRS score  $\geq 4$ .

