#### **7.5.1.5. Skin Pain Numeric Rating Scale**

The Skin Pain NRS is a daily participant-reported measure (24-hour or 7-day recall) of the worst level of pain intensity from 0 (no pain) to 10 (worst pain imaginable). Participants will be asked to rate the pain intensity by selecting a number that best describes the worst level of pain in the past 24 hours via the eDiary during the VC period and in the past 7 days via tablet at the site during the VCE period.

The baseline Skin Pain NRS score for VC period will be determined by averaging the 7 daily NRS scores directly before Day 1 (Day -7 to Day -1) for all the by-visit summaries. The by-visit Skin Pain NRS score for postbaseline visits will be determined by averaging the 7 daily NRS scores directly before the visit day. If 4 or more daily scores are missing (out of the 7), the Skin Pain NRS score at the visit will be set to missing. For all the daily pain-related analyses, baseline will be defined as the last available pain NRS score during the last week prior to Day 1 (from Day -7 to Day -1).

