### **7.5.2. Secondary Efficacy Analysis**

All secondary efficacy analyses will be conducted in the VC and VCE DB periods, with the exception that proportion of participants achieving IGA-TS and EASI75 which will also be summarized by visit in the escape arm for participants that entered escape arm at Week 8.

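### After Week 8, ITCH4 and change in itch and skin pain have no like-for-like baseline: a single worst-in-7-days rating would be set against a mean of daily scores, and SAP Table 1 and Appendix A disagree on ITCH4 there

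*SAP*

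**What the plan says.** **Endpoints.** SAP Table 1 lists "The binary response status of ITCH4 from baseline at each postbaseline visit except Week 8"; Protocol section 3 has the same endpoint as a proportion. Both tables also ask for change in the Itch NRS and Skin Pain NRS scores at every postbaseline visit. On period, SAP 7.5.2 states: "All secondary efficacy analyses will be conducted in the VC and VCE DB periods". SAP 7.5.2.1 includes change from baseline for both scores in its by-visit summaries and keeps summary statistics for the VCE DB period. SAP 7.1 adds the safety follow-up visit to by-visit analyses where data exist.

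**Baseline and VC visits.** The daily item asks for the number "that best describes their worst level of itching in the past 24 hours". SAP 7.4.1.1 then says: "The Itch NRS score for baseline will be determined by averaging the 7 daily NRS scores directly before Day 1". VC visits use the mean of the seven daily scores before the visit. SAP 7.5.1.5 defines skin pain the same way.

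**Extension and follow-up.** Itch becomes one rating of the "worst level of itching in the past 7 days via the tablet during Protocol-defined clinic visits during the VCE period". Pain is rated as the worst level "in the past 7 days via tablet at the site during the VCE period". Protocol Table 4 captures both only at site visits, including follow-up. Protocol Table 3 schedules no 7-day-recall item at screening, Day 1 or Week 8.

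**Outputs.** In Appendix A, Table 2.3.1 and Figure 4.3.1 (ITCH4) and Figure 4.3.4 (itch change) are limited to the VC period. VCE itch and pain scores have their own tables (2.3.5.2, 2.6.1.2).

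**The concern.** Improvement is a difference, so both scores should measure the same thing. Up to Week 8 they do: a weekly mean minus a weekly mean. From Week 12 the stated endpoints become a weekly mean at baseline minus a weekly worst at follow-up. A participant whose itch has not changed since Week 8 would then appear to have worsened at Week 12 simply because the question changed. The extension exists to assess durability of response, so a step down at exactly that visit invites the wrong conclusion. Skin pain is affected in the same way, and any output that runs across both periods mixes the two instruments without saying so.

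**Working it through.** **1. Which score exists when.**

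| Visit | Itch and skin-pain score available |
|---|---|
| Baseline (Day -7 to Day -1) | Mean of seven daily 24-hour worst scores |
| Weeks 2, 4, 8 | Mean of seven daily 24-hour worst scores |
| Weeks 12, 16, 20, 24 and follow-up | One rating of the worst in 7 days |

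No alternative baseline in the plan repairs this. Taking Week 8 as the VCE baseline (Protocol Table 3, footnote d) gives another daily mean. The general rule in SAP 4.1.3 takes the last value before first application, and no 7-day-recall score exists by then. The averaging rule for postbaseline visits cannot be applied in the VCE because no daily itch or pain scores are collected there.

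**2. Nearest stated figure.** The plan gives no figure for VCE itch. The closest is power above 95% for ITCH4 at Week 8 (50% vs 15%). With 225 randomized 2:1, that is 150 vs 75. Exact enumeration of the two-sided Fisher test at 0.05 gives 99.98%, so the statement reproduces. That endpoint uses daily means at both times and is not in question.

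**3. Direction.** If recall is accurate, the 7-day worst is the maximum of the seven daily worst scores, and a maximum is never below the mean. For seven independent normal values, E(max - mean) = 1.35 x within-person SD. Before the 0-10 limits this is 1.35 x 0.5 = 0.7, 1.35 x 1.0 = 1.4 and 1.35 x 1.5 = 2.0 points. At SD 0 it is zero.

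**4. Effect on ITCH4.** The documents give no day-to-day SD, so it is varied. Simulation assumptions: integer 0-10 daily scores; baseline mean 7, between-person SD 1.5, restricted to baseline of at least 4; SD of true change 2.5. The mean change was set so that the like-for-like rate was about 50% in one group and 15% in the other.

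| Within-person SD | Mean minus mean | Baseline mean minus follow-up worst | Baseline worst minus follow-up worst |
|---|---|---|---|
| 0 | 50% / 15% | 50% / 15% | 50% / 15% |
| 0.5 | 50% / 15% | 40% / 10% | 57% / 20% |
| 1.0 | 50% / 15% | 32% / 7% | 56% / 20% |
| 1.5 | 50% / 15% | 24% / 5% | 54% / 20% |

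Mean improvement on the mixed scales is lower by about 0, 0.6, 1.2 and 1.7 points.

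**5. Second set of assumptions.** Baseline mean 6.5, between-person SD 1.6, day-to-day SD 0.8-1.6 with lag correlation 0-0.4, mean true change 4 points with SD 2.5. ITCH4 is 48-50% like for like, 22-37% on mixed scales, and 53-57% with the 7-day maximum at both times. Together with step 4, about 50% reads about 22-40%.

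**6. Between arms.** At within-person SD 1.0 the difference in mean change is 3.77 - 1.41 = 2.36 points like for like and 2.60 - 0.22 = 2.38 on mixed scales, so it is nearly unchanged. The difference in ITCH4 rates shrinks from 50 - 15 = 35 points to 40 - 10 = 30, 32 - 7 = 25 and 24 - 5 = 19 (about 20 before rounding) at SD 0.5, 1.0 and 1.5.

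**7. Outputs that span both instruments.** Figure 4.6.2 (skin-pain change) carries no period limit. Tables 2.2.17.1 and 2.2.17.2 use an Itch NRS threshold of 4 that rests on a weekly mean up to Week 8 and on a weekly worst from Week 12.

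**The case against.** The strongest reply is that the planned outputs do not make the comparison for ITCH4. The ITCH4 table and figure and the itch-change figure are VC only. VCE itch has a separate descriptive table and a plot of scores. SAP 7.5.1.5 words the averaged pain baseline as one for the VC period, and SAP 7.1 analyses change only where it is available. On that reading the VCE scores are simply shown as observed. This stands to the extent that a reader who infers that mixed-scale ITCH4 will certainly be reported goes beyond the documents. It does not remove the point. Table 1 still requires ITCH4 at those visits, SAP 11.1 records no removal, Appendix A describes its list as a guideline, 7.5.2.1 asks for change, and Figure 4.6.2 is unrestricted.

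Three further objections have force:

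- A recalled worst is not a computed maximum, so the direction is conditional on recall tracking the worst day.
- Both arms answer the same item. If day-to-day variability is equal, the between-arm difference in mean change is almost preserved. The VCE response criterion is EASI50, and continuous VCE measures receive summary statistics only.
- The concurrent-criteria endpoint also needs IGA of at least 3, EASI of at least 16, BSA of at least 10% and DLQI above 10. While EASI50 is held, EASI of at least 16 implies a baseline of at least 2 x 16 = 32. Itch is unlikely to be the deciding component, and no effect on the composite has been shown.

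**Conclusion.** The mismatch is real and should be corrected. The plan calls for ITCH4 and change from baseline after Week 8 but defines no baseline on the instrument used there, and Table 1 and Appendix A disagree on whether VCE ITCH4 is produced. Computed as written, within-arm improvement is understated if the recalled score tracks the worst day.

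The size rests on assumptions. With within-person SD 0.5-1.6 and true change varying with SD 2.5, ITCH4 of about 50% would read about 22-40%. With no day-to-day variation there is no loss.

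Two stronger readings are not supported. A reader might infer a near-collapse of ITCH4, to 3-12%, but that arises only if every participant improves by exactly 4 points and so sits on the threshold. A reader might also infer that the trial's main conclusions are at risk. They are not: the coprimary endpoints do not use itch, the key secondary endpoints (Week 8 and Days 7, 3 and 2) use daily scores throughout, and VCE itch lies outside the alpha-controlled sequence.

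**What to change.** - Present the VC series (mean of daily 24-hour scores) and the VCE and follow-up series (7-day recall) separately for itch and skin pain, including in Figure 4.6.2.
- Do not compute ITCH4 or change in the VCE or at follow-up against the daily-mean baseline. Report the 7-day-recall scores as observed values.
- If ITCH4 or change is kept there, use as baseline the maximum of the Day -7 to Day -1 daily scores, with the same requirement of at least 4 of 7 days, and label it a derived approximation.
- Footnote the change of instrument in Tables 2.2.17.1 and 2.2.17.2. Recomputing their Week 2 to Week 8 values is not justified by any effect shown.
- Align Table 1, 7.5.1.4, 7.5.1.5, 7.5.2 and Appendix A, and record the change in 11.1. Leave the key secondary ITCH4 endpoints as they are.

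The cost is SAP wording and, if the derived baseline is used, one variable per score from eDiary data already collected. The downside is that VCE ITCH4 is either dropped or rests on an approximation. That approximation tends to raise ITCH4 modestly (53-57% against 48-50% in step 5). It also depends on diary completeness: taking the maximum over 4 rather than 7 baseline days lowered ITCH4 by about 4 to 12 points across the simulation assumptions tried.

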#### **7.5.1.5. Skin Pain Numeric Rating Scale**

The Skin Pain NRS is a daily participant-reported measure (24-hour or 7-day recall) of the worst level of pain intensity from 0 (no pain) to 10 (worst pain imaginable). Participants will be asked to rate the pain intensity by selecting a number that best describes the worst level of pain in the past 24 hours via the eDiary during the VC period and in the past 7 days via tablet at the site during the VCE period.

The baseline Skin Pain NRS score for VC period will be determined by averaging the 7 daily NRS scores directly before Day 1 (Day -7 to Day -1) for all the by-visit summaries. The by-visit Skin Pain NRS score for postbaseline visits will be determined by averaging the 7 daily NRS scores directly before the visit day. If 4 or more daily scores are missing (out of the 7), the Skin Pain NRS score at the visit will be set to missing. For all the daily pain-related analyses, baseline will be defined as the last available pain NRS score during the last week prior to Day 1 (from Day -7 to Day -1).

#### **7.5.1.6. Dermatology Life Quality Index**

The DLQI is a simple, 10-question validated questionnaire to measure how much the skin problem has affected the participant over the previous 7 days.

The scoring of each question is as follows: Very much = 3; A lot = 2; A little = 1; Not at all = 0; Not relevant = 0; Question 7, 'prevented work or studying' = 3.

The following imputation will be applied for incorrectly completed questionnaires:

- If one question is left unanswered, this is scored 0 and the scores are summed and expressed as usual out of a maximum of 30.
- If 2 or more questions are left unanswered the questionnaire is not scored.
- If Question 7 is answered 'yes' this is scored 3. If Question 7 is answered 'no' but then either 'a lot' or 'a little' is ticked, this is then scored 2 or 1. If "not relevant" is ticked, the score for Question 7 is 0. If it is answered 'no', but the second half is left incomplete, the score will remain 0.
- For DLQI 6 subscales, if the answer to one question in a subscale is missing, that subscale should not be scored.

The DLQI is calculated by summing the score of each question resulting in a maximum of 30 and a minimum of 0. The higher the score, the more quality of life is impaired.

The meaning of total DLQI scores can be categorized as follows:

- 0-1 = No effect
- 2-5 = Small effect
- 6-10 = Moderate effect
- 11-20 = Very large effect
- 21-30 = extremely large effect

A change from baseline in DLQI score of at least 4 points is considered clinically important (Basra et al 2015). The questionnaire is also analyzed under 6 subscales as follows:

- Symptoms and feelings (Questions 1 and 2)
- Daily activities (Questions 3 and 4)
- Leisure (Questions 5 and 6)
- Work and school (Question 7)
- Personal relations (Questions 8 and 9)
- Treatment (Question 10)

#### **7.5.1.7. Patient-Oriented Eczema Measure**

The POEM is a 7-question QoL assessment used for monitoring atopic eczema severity, focusing on the illness as experienced by the participant. The questionnaire asks how many days the participant has been bothered by various aspects of their skin condition during the past week. The response options and corresponding scoring questionnaires are no days (0), 1 to 2 days (1), 3 to 4 days (2), 5 to 6 days (3), and every day (4), with a range in total score of 0 to 28. If 1 question is missing, this question is scored 0 and the total score is calculated as summing the rest of the questions and expressed as usual out of a maximum of 28. If 2 or more questions are missing, the questionnaire is not scored (Charman et al 2004).

The meaning of POEM scores can be categorized as follows: 0 to 2 (clear/almost clear), 3 to 7 (mild eczema), 8 to 16 (moderate eczema), 17 to 24 (severe eczema), and 25 to 28 (very severe eczema; Charman et al 2013).

#### **7.5.1.8. EQ-5D-5L**

The EQ-5D is a validated, self-administered, generic utility questionnaire wherein participants rate their current health state based on the following criteria (dimensions): mobility, self-care, usual activities, pain/discomfort, and anxiety/depression.

The 5L indicates that for each dimension, there are 5 levels, which are as follows: no problems, slight problems, moderate problems, severe problems, and extreme problems.

During all VC period study visits (starting at Day 1) and at specific VCE visits, the participant will be asked to indicate his/her health state over the past 7 days.

Missing values will not be imputed. The categorical outcomes for the 5 dimensions (mobility, self-care, usual activity, pain/discomfort, and anxiety/depression) will be summarized. The change from baseline in EQ-5D VAS score will be summarized.

#### **7.5.1.9. Work Productivity and Activity Impairment Questionnaire: Atopic Dermatitis**

The WPAI-AD questionnaire is a validated 6-item instrument that measures the effect of overall health and specific symptoms on productivity at work and regular activities outside of it during the past 7 days (Reilly et al 1993).

The WPAI outcomes are expressed as impairment percentages, with higher numbers indicating greater impairment and less productivity (ie, worse outcomes) as follows:

Questions:

- 1 = currently employed
- 2 = hours missed due to AD
- 3 = hours missed other reasons
- 4 = hours actually worked
- 5 = degree AD-affected productivity while working
- 6 = degree AD-affected regular activities

Scores:

- Multiply scores by 100 to express in percentages.
  - Percent work time missed due to AD:  $Q2 / (Q2 + Q4)$
  - Percent impairment while working due to AD:  $Q5 / 10$
  - Percent overall work impairment due to AD:  $Q2 / (Q2 + Q4) + [(1 - (Q2 / (Q2 + Q4))) \times (Q5/10)]$
  - Percent activity impairment due to AD:  $Q6 / 10$

These impairment percentages will be summarized by visit and by treatment for those patients who are currently employed. Missing values will not be imputed.

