
To evaluate quality of life and other PROs in participants with moderate AD who had an inadequate response to, or are intolerant to, or contraindicated to TCSs and TCIs.
	
 • Proportion of participants who achieve ≥ 4-point improvement in DLQI from baseline at each postbaseline visit. • Change from baseline in the following scores at each postbaseline visit: 
 – DLQI – POEM – EQ-5D-5L – HADS – PROMIS Short Form – Sleep-Related Impairment (8a – 7-day recall) – PROMIS Short Form – Sleep Disturbance (8b – 7-day recall) • Change from baseline score at Weeks 8 and 24 in WPAI-AD.

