8.2.6.6. Work Productivity and Activity Impairment Questionnaire: Atopic Dermatitis

The WPAI-AD questionnaire (refer to the SRM) is a validated 6-item instrument, completed (via tablet; see [Table 3](#) and [Table 4](#)), that measures the effect of overall health and specific symptoms on productivity at work and regular activities outside of it during the past 7 days ([Reilly et al 1993](#)).

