## **5.3. Analysis Populations**

### **5.3.1. Intent-to-Treat Population**

All participants who are randomized to the study constitute the ITT population. Treatment groups for this population will be defined according to the treatment assignment at the time of randomization regardless of the actual study treatment the participant might apply during their participation in the study.

The ITT population will be used for the summary of all efficacy data in the VC and VCE DB periods.

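### The SAP limits all four WPAI-AD scores to employed participants, so activity impairment goes unsummarized for everyone not in work

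*SAP*

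**What the plan says.** SAP 7.5.1.9 introduces the scores with "The WPAI outcomes are expressed as impairment percentages" and lists four: work time missed, impairment while working, overall work impairment, and "Percent activity impairment due to AD". The items behind them include "1 = currently employed" (Q1) and "6 = degree AD-affected regular activities" (Q6). The section then states the reporting set: "These impairment percentages will be summarized by visit and by treatment for those patients who are currently employed". It adds that missing values are not imputed.

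Elsewhere, the documents attach no employment condition:

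- Protocol Section 3 and SAP Table 1 give the endpoint as "Change from baseline score at Weeks 8 and 24 in WPAI-AD".
- Protocol 8.2.6.6 says the instrument "measures the effect of overall health and specific symptoms on productivity at work and regular activities outside of it during the past 7 days".
- SAP 5.3.1 says "The ITT population will be used for the summary of all efficacy data in the VC and VCE DB periods".
- SAP Appendix A plans a single WPAI-AD table, 2.10.1, and labels its population ITT.

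**The concern.** The reporting sentence points back to the whole list of four scores. An employment restriction is natural for the three work scores. It has no basis for activity impairment, which is the part of the instrument meant to cover life outside work and can be scored for anyone who answers Q6.

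Followed as written, the rule reports one component of a secondary endpoint in a selected subset. Participants without a job are to be expected: eligibility sets no employment requirement and no upper age limit, and SAP 7.3.3 plans a subgroup aged 65 or over. The rule also does not say at which visit employment is judged. If it is judged visit by visit, participants whose status changes would enter and leave the summary between baseline, Week 8 and Week 24, which disturbs a change-from-baseline measure.

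**Working it through.** **1. Which scores need employment?** Formulas from SAP 7.5.1.9, each multiplied by 100:

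| Score | Formula | Work items used | Participant with no work hours (Q2 = Q4 = 0) |
|---|---|---|---|
| Work time missed | Q2/(Q2+Q4) | Q2, Q4 | 0/0, undefined |
| Impairment while working | Q5/10 | Q5 | Not meaningful |
| Overall work impairment | Q2/(Q2+Q4) + [1 − Q2/(Q2+Q4)] × Q5/10 | Q2, Q4, Q5 | Undefined |
| Activity impairment | Q6/10 | None | Computable; for example Q6 = 7 gives 70% |

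For activity impairment, the exclusion therefore comes only from the reporting sentence and not from the scoring.

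**2. Does another provision restore the excluded participants?** The endpoint definition, SAP 5.3.1 and Table 2.10.1 all point to the full ITT population, but 7.5.1.9 is the specific rule and would normally override them. No separate activity-impairment table is planned for all participants. Missing values are not imputed, so nothing re-enters that way. SAP 11.1 does not list the restriction as a change from the protocol.

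**3. Size, as an illustration.** There is no figure in the plan to reproduce. Inputs: about 225 participants randomized 2:1, that is about 150 and 75. The share employed, e, is not given and is assumed. With the same e and the same standard deviation in both arms, the standard error of the between-arm difference grows by

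sqrt[(1/(150e) + 1/(75e)) / (1/150 + 1/75)] = 1/sqrt(e).

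| Assumed e | Participants summarized (225 × e) | Left out | Standard error factor |
|---|---|---|---|
| 0.5 | 112.5 | 112.5 | 1.41 |
| 0.6 | 135 | 90 | 1.29 |
| 0.7 | 157.5 | 67.5 | 1.20 |
| 0.8 | 180 | 45 | 1.12 |
| 0.9 | 202.5 | 22.5 | 1.05 |

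For e = 0.6: (1/90 + 1/45)/(1/150 + 1/75) = 0.0333/0.0200 = 1.667, and its square root is 1.29.

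The counts are ceilings. By Week 24 fewer participants contribute, because SAP 7.5.2 confines the secondary analyses to the VC and VCE double-blind periods, which leaves out escape-arm data on WPAI-AD. The standard error factor does not depend on that attrition if the employed share among those remaining is the same.

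**The case against.** The case for leaving the text alone has several parts.

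- **The data are not lost.** WPAI-AD is scheduled without an employment condition at Day 1, Week 8, Week 24 and safety follow-up, and Listing 2.6.10 is planned. This stands: the loss is from the summaries, not from the database.
- **It may be loose drafting.** The ITT label on Table 2.10.1 carries no employed-only qualifier, while other rows of Appendix A do state restricted populations. Perhaps only the work scores were meant. That is possible, but a programmer has to act on the text, and the text makes no exception.
- **Q6 may not be asked of everyone.** The questionnaire and its routing are in the Study Reference Manual, which is not available here. The formula shows that Q6 can be scored without work items; that participants not in work are asked it is an inference, supported by the protocol's description of the instrument.
- **The employment share is assumed.** True, and the table should be read only as an illustration. The mismatch between rule and score does not depend on the share.
- **The impact is small.** WPAI-AD is outside the fixed testing sequence, an MMRM at Week 8 is optional, and the double-blind extension is summarized descriptively. If employment is taken at baseline, the employed form a pre-treatment subgroup in which the randomized comparison remains valid, so the cost is precision and coverage, not bias. This stands, and it limits the severity.
- **Movement between visits is conditional.** It arises only if employment is judged at each visit, which the SAP leaves open.

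**Conclusion.** The concern holds. SAP 7.5.1.9 restricts all four scores to employed participants, and for activity impairment the restriction is unnecessary and at odds with the endpoint definition, SAP 5.3.1 and the ITT label on Table 2.10.1. Under an assumed 60% to 80% employed, the activity summary would use at most 135 to 180 of 225 participants, with a standard error 29% to 12% larger than it need be; widening the assumption to 50% to 90% gives 41% to 5%. These figures assume the same employed share and the same standard deviation in both arms, and that participants not in work answer Q6.

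The coprimary and key secondary conclusions are unaffected. This is a worthwhile correction of low severity.

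**What to change.** Amend the reporting sentence in SAP 7.5.1.9 so that the employment restriction applies only to work time missed, impairment while working and overall work impairment. State that activity impairment (Q6/10) is summarized by visit and treatment for all ITT participants with a Q6 response. For the three work scores, the same sentence should say which visit's answer to Q1 defines employment, because limiting the restriction does not settle that question for them. A footnote to Table 2.10.1 can give the denominator for each score.

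The cost is one SAP sentence and a table footnote. No new data, visits or protocol change are needed, and no controlled test is affected.
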